2. OBJECTIVES

To further evaluate the safety and efficacy of Acthar in subjects with severe keratitis when treated with Acthar gel.

2.1. Assessments of Efficacy

Table 2: Efficacy Assessments for Study MNK14084113

Efficacy Assessments	
Corneal Staining	Inferior, superior, central and total cornea regions as measured by the Ora Calibra™ Corneal Staining Scale (0 - 4)
Conjunctival Staining	Nasal, temporal and total conjunctiva regions as measured by the Ora Calibra™ Conjunctival Staining Scale (0-4)
Conjunctival Redness	As measured by the Ora Calibra™ Conjunctival Redness Scale (0 - 4)
Tear Production	Schirmer's Test (mm)
Tear Film Stability	Tear Film Break-Up Time (seconds)
Dryness	As measured by the 0 - 100 mm Visual Analogue Scale (VAS)
Ocular Discomfort	As measured by the Ora Calibra™ Ocular Discomfort Scale (0 - 4)
Ocular discomfort, dryness, grittiness, burning and stinging	As measured by the Ora Calibra™ 4-symptom Questionnaire (0 - 5)
Quality of Life	As measured by IDEEL (Impact of Dry Eye on Everyday Life)
Immunological protein assay	Protein assay to detect levels of the cytokine array [interleukin 1,6,17; interferon- γ]; ratio of T helper cells to T regulatory cells

2.2. Assessment of Safety

The frequency of adverse events (AEs), AEs of special interest (AESIs); clinical laboratory tests; metabolic panel; vital signs; physical examination; and ophthalmic findings (best corrected visual acuity, intraocular pressure, slit lamp examination, undilated eye examination) will be used to detect the presence of a safety signal(s).

2.3. Outcome Measures

The primary outcome measure is the proportion of responders who improved on the IDEEL score. There are no secondary outcome measures.

3. STUDY DESIGN

3.1. Overall Design

This is a multicenter, multiple dose, open-label study to examine the efficacy of Acthar in adult subjects 18 years of age or older with a diagnosis of keratitis sicca. Up to 36 subjects with severe or recalcitrant keratitis who did not respond or tolerate treatment with topical cyclosporine or any immunosuppressant to treat keratitis will be enrolled. Subjects who meet entry criteria will be treated with Acthar 1 mL (80 units [U]) subcutaneously (SC) 2x (twice) per week for 12 weeks, followed by a 4 week taper period of 40 U 2x/week for 2 weeks then 40 U 1x/week for 2 more weeks. Subjects will be reassessed at an in-clinic safety visit, 4 weeks after the last treatment dose for AE assessments, and concomitant medication use. Endpoints will be measured at Baseline and all other visits.

3.2. Duration of Subject Participation

Subjects will participate in the study for approximately 22 weeks, including a screening period of up to 28 days, an active treatment period of 12 weeks, an Acthar taper period of 4 weeks, and a follow up in-person safety visit 4 weeks after the last treatment dose of study drug.

3.3. Duration of Study

The duration of the study from first subject first visit to last subject last visit will be dependent on the ability of the sites to identify and enroll eligible subjects. The entire study is expected to require approximately 1 year to complete.

3.4. Number of Subjects

Up to 36 subjects will be enrolled in this study at approximately 6 sites in the US.

3.5. Treatment/Dose Rationale

According to the Acthar Package Insert, the dosage should be individualized depending on the disease under treatment and the medical condition of the patient. The usual dose of Acthar is 40 to 80 U (0.5 to 1 mL) given subcutaneously every 24 to 72 hours ([Acthar® Gel Package Insert, 2019](#)). In a survey of patients with ocular inflammatory disease that had been treated with Acthar and had registered with the sponsor's patient support services, those with keratitis were most often treated with a subcutaneous injection of 80 U mL of Acthar 2x/week. To take into account the patient survey results, 80 U 2x/week was selected as the dose for this study. ([Mallinckrodt Acthar Data Compendium, 2018](#)).

Following the 12 week period of treatment with 80 U, Acthar will be tapered over a 4 week period. The 80 U dose will be reduced to 40 U 2x/week for 2 weeks, followed by 40 U 1x/week for 2 additional weeks.

3.6. End of Study Definition

A subject is considered to have completed the study if the subject has completed the final assessments at Visit 7.

The end of the study is defined as the completion of the final assessment for the last subject enrolled in the trial.

4. STUDY POPULATION

Prospective approval of protocol deviations in recruitment and enrollment criteria, also known as protocol waiver or exemption, is not permitted.

4.1. Inclusion Criteria

To be eligible to participate in the study, at the Screening Visit and the Baseline Visit (except as noted below) each subject must:

1. Be adequately informed and understand the nature and risks of the study and must be able to provide a signature and date on the ICF;
2. Be 18 years of age or older at the Screening Visit and may be male or female;
3. Have normal lid anatomy;
4. Have a reported history of severe keratitis in one or both eyes and a history of previous treatment for keratitis within the previous 6 months;
5. Did not respond adequately or did not tolerate previous treatment with topical cyclosporine or LFA-1 antagonist;
6. Have all the following in at least one eye (the same eye) at screening and baseline:
 - a. Have an inferior corneal fluorescein staining score of at least 2 points in any field (Ora Calibra™ Scale) in at least one eye at the Screening and Baseline visits;
 - b. Have a sum corneal fluorescein staining score ≥ 4 , based on the sum of the central, superior, and inferior regions of the cornea (Ora Calibra™ Scale) in at least one eye at the Screening and Baseline Visits;
 - c. Have a sum lissamine green conjunctival score of ≥ 2 , based on the sum of the temporal and nasal regions of the conjunctiva (Ora Calibra™ Scale) in at least one eye at Screening and Baseline visits;
 - d. Have a conjunctival redness score ≥ 1 (0-4 point Ora scale) in at least one eye at the Screening and Baseline Visits;
 - e. Have a Schirmer score ≥ 1 mm and ≤ 10 mm/5min in at least one eye at the Screening and Baseline Visits;
 - f. Have an Ocular Discomfort Score (ODS) of ≥ 2 (0-4 point Ora scale) in at least one eye at the Screening and Baseline Visits;
7. If female, of nonchildbearing potential (history of hysterectomy, bilateral oophorectomy, bilateral tubal ligation; or postmenopausal with no history of menstrual flow in the 12 months prior to the Screening Visit); or, if of childbearing potential, be nonpregnant, nonlactating, and agree to use 2 forms of effective contraception when with a male partner for the duration of the study (through Visit 6). Acceptable forms of contraception include hormonal measures (oral contraceptive pills, contraceptive patch, contraceptive ring, injections), intrauterine devices, double barrier method (condom plus diaphragm, condom or diaphragm plus spermicidal gel or foam, surgical sterilization of the male partner), and abstinence;

8. If male with reproductive potential, agree to use 2 forms of effective contraception (abstinence, surgical sterilization [vasectomy], or condom with spermicide) with a female partner for the duration of the study (through Visit 6);
9. Subjects must have a mean systolic blood pressure \leq 150 mm Hg and a diastolic blood pressure of \leq 90 mm Hg determined by the average of 2 seated readings taken at least 5 minutes apart at the Screening and Baseline Visits;
10. Be able to communicate effectively with study personnel;
11. Be able and willing to follow all protocol requirements and study restrictions;
12. Be able and willing to return for all study visits

4.2. Exclusion Criteria

A subject is ineligible for study participation if the subject meets any of the following criteria at the Screening or Baseline Visit:

1. Subject is from a vulnerable population, as defined by the US CFR Title 45, Part 46, Section 46.111(b) and other local and national regulations, including but not limited to, employees (temporary, part-time, full time, etc.) or a family member of the research staff conducting the study, or of the sponsor, or of the clinical research organization, or of the IRB/IEC;
2. Have any ocular condition that, in the opinion of the investigator, could affect study parameters including, but not limited to, glaucoma, diabetic retinopathy, blepharitis, meibomian gland disease, lid margin inflammation, ocular allergies, follicular conjunctivitis, iritis, uveitis, neuropathic pain and/or active ocular inflammation not related to keratitis;
3. Have a history of laser-assisted in situ keratomileusis (LASIK) or similar type of corneal refractive surgery within 12 months prior to the Baseline visit, and/or any other ocular surgical procedure (eg, cataract surgery, eyelid surgery) within 12 months prior to the Baseline Visit; or any scheduled ocular surgical procedure during the study phase;
4. Have active or any history of ocular herpes; and other ocular infection within 30 days prior to the Baseline visit;
5. Have current punctal plugs (within 30 days prior to Screening visit), punctal occlusion, or history of nasolacrimal duct obstruction;
6. Be unwilling to avoid wearing contact lenses for 7 days prior to the Screening visit and for the duration of the study phase;
7. Have best corrected visual acuity < 0.7 Logarithm of the Minimum Angle of Resolution (logMAR) in each eye at the Screening and Baseline Visits;
8. Use prohibited prescription or over-the-counter (OTC) medications or devices and be unable to discontinue their use for the required period before entry into the study as follows:

- a. Ophthalmic cyclosporine (Restasis®) or ophthalmic lymphocyte function-associated antigen-1 (LFA-1) antagonist (Xiidra®): 12 weeks prior to the Screening visit;
- b. Corticosteroids (topical and systemic), ocular autologous serum, antibiotics (topical and systemic), mast cell stabilizers (topical and systemic), vasoconstrictors (topical and systemic): 30 days prior to the Screening visit;
- c. Systemic tetracycline compounds (tetracycline, doxycycline or minocycline), unless the dose has been stable for at least 30 days prior to the Screening visit and will remain stable during the study phase, in which case this is permitted;
- d. Any medication (topical and systemic) known to cause ocular drying, such as the use of systemic anticholinergic medications (eg, antihistamines and antidepressants), unless the dose has been stable for at least 30 days prior to the Screening visit and will remain stable during the study phase;
- e. Antihistamines (topical and systemic): 7 days prior to the Screening visit;
- f. Topical or nasal vasoconstrictors within 14 days prior to screening;
- g. Unable to refrain from using artificial tears
- h. Subject has received glucocorticosteroid implants such as Retisert®, Iluvien®, or Yutiq™ within 3 years prior to the Baseline Visit or has had complications related to the device and/or subject has had a glucocorticoid implant removed within 90 days prior to the Baseline Visit or has had complications related to the removal of the device;
 - i. Any FDA-approved medical devices other than punctal plugs (eg Lipiflow® and Truetear®) for dry eye 12 weeks prior to the Screening visit;
- 9. Subject is unwilling to receive, or is intolerant of, SC injections;
- 10. Subject has a history of sensitivity to ACTH preparations or sensitivity to porcine protein products;
- 11. Subject has Type 1 or Type 2 diabetes mellitus or is taking antidiabetic medication (a history of gestational diabetes mellitus is not exclusionary);
- 12. Subject has proliferative or severe nonproliferative diabetic retinopathy, clinically significant macular edema due to diabetic retinopathy, or neovascular/wet age-related macular degeneration;
- 13. Subject has a history of chronic active hepatitis including active or chronic hepatitis B, or acute or chronic hepatitis C;
- 14. Subject has a history of tuberculosis (TB) infection, any signs/symptoms of TB, or any close contact with an individual with an active TB infection;
- 15. Subject has an active corneal infection, any other systemic infection;
- 16. Subject has received a live or attenuated-live vaccine within 30 days prior to screening;
- 17. Subject had ocular trauma, penetrating intraocular surgery, refractive surgery, corneal transplantation, or eyelid surgery within 12 weeks prior to screening;

18. Subject is unwilling to abstain from eyelash growth medications for the duration of the trial;
19. Subject is under treatment with any corticosteroids, immunosuppressants, immunomodulators, or biologic agents for a concomitant condition (eg, rheumatoid arthritis under treatment with a tumor necrosis factor- alpha [TNF- α] drug). Subjects are specifically excluded for any of the following;
 - a. Subject has received intraocular or periocular corticosteroids within 30 days prior to Baseline Visit;
 - b. Subject has received Ozurdex® (dexamethasone implant) within 6 months prior to the Baseline Visit;
 - c. Subject has received intravitreal anti-VEGF therapy within 45 days of the Baseline Visit with Lucentis® (ranibizumab) or Avastin® (bevacizumab) or has received anti-VEGF Trap (aflibercept) within 60 days of the Baseline Visit;
 - d. All others, subject has received treatment within 30 days prior to baseline;
20. Subject has any known contraindication(s) to [Acthar® Gel Package Insert, 2019](#) including, but not limited to:
 - a. Any known history of scleroderma, osteoporosis, or ocular herpes simplex. For the purposes of this study, osteoporosis is defined as evidence of current vertebral or long bone fracture, or lumbar T-score > 2.0 standard deviations (SD) below the mean of the reference population;
 - b. Any primary adrenocortical insufficiency, or adrenal cortical hyperfunction,
 - c. Any current congestive heart failure (defined as New York Heart Association Functional Class III to IV),
 - d. Peptic ulcer (within 24 weeks prior to the Screening Visit);
 - e. Recent major surgery (within 24 weeks prior to the Screening Visit);
21. Subject has a clinically significant infection requiring administration of intravenous antibiotics or hospitalization in the 4 weeks prior to the Screening Visit or between the Screening Visit and the first dose of study drug;
22. Subject has known immune-compromised status (not related to disease/condition under study), including but not limited to, individuals who have undergone organ transplantation or who are known to be positive for the human immunodeficiency virus;
23. Subject has any solid tumor malignancy currently diagnosed or undergoing therapy, or has received therapy for any solid tumor malignancy in the 5 years prior to the Screening Visit; with the exception of treated and cured basal cell carcinoma, treated and cured squamous cell carcinoma of the skin, and treated and cured carcinoma in situ of the cervix;
24. Subject has a diagnosis of, is undergoing therapy for, or has received therapy for a hematologic malignancy in the 5 years prior to the Screening Visit;

25. Subject has current or recent (within 24 weeks prior to the Screening Visit) drug or alcohol abuse as defined in [Diagnostic and Statistical Manual of Mental Disorders , 2013](#), Fifth Edition, Diagnostic Criteria for Drug and Alcohol Abuse;
26. Subject has any of the following laboratory abnormalities at the Screening Visit:
 - a. Hemoglobin \leq 8.0 g/dL;
 - b. Platelet count \leq 50,000 cells/ μ L;
 - c. Absolute neutrophil count (ANC) \leq 1000 cells/ μ L;
 - d. Aspartate aminotransferase (AST), alanine aminotransferase (ALT), or total bilirubin $>$ 2 times upper limit of normal (ULN);
 - e. Glycosylated hemoglobin (HbA1c) $>$ 6.5;
 - f. Positive Hepatitis B surface antigen (HBsAg) or Hepatitis B core antibody (HBcAb), or positive or indeterminant Hepatitis C virus antibody (HCV);
 - g. Systolic blood pressure $>$ 150 mm Hg and diastolic blood pressure $>$ 90 mm Hg (average of 2 assessments) at the Screening or Baseline Visits does not qualify for the study;
 - h. Positive or indeterminate interferon gamma release assay (IGRA) for TB;
27. Subject has any other clinically significant disease, disorder or laboratory abnormality (including those listed on the Prescribing Information Section 5: Warnings and Precautions [[Acthar® Gel Package Insert, 2019](#)]) which, in the opinion of the investigator (by its nature or by being inadequately controlled), might put the patient at risk due to participation in the study, or may influence the results of the study or the subject's ability to complete the study;
28. Subject is participating in or plans to participate in any other interventional research study from the time of screening and throughout this study.

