1. BACKGROUND INFORMATION AND RATIONALE

1.1. Disease/Condition Under Study

Keratitis is a painful inflammation of the cornea which can result in partial or total loss of vision if left untreated and is a significant cause of ocular morbidity around the world ([Sharma, 2001](#)). It can result from infectious agents (eg, microbes including bacteria, fungi, amebae, and viruses) ([Collier, 2010](#)) or from noninfectious causes (eg, eye trauma, chemical exposure, and ultraviolet exposure). Conditions that affect the integrity of the ocular surface epithelium (exposure keratitis, neurotrophic keratitis, keratomalacia, recurrent corneal erosions) may also lead to development of sterile corneal ulcers. Non-infectious corneal ulcers may be associated with various collagen vascular or other autoimmune diseases, sometimes as the presenting sign of the disease ([Donzis, 1987](#)).

As described in the Package Insert, Acthar® Gel (repository corticotropin injection, hereafter referred to as Acthar) is a naturally sourced complex mixture of adrenocorticotrophic hormone (ACTH) analogues and other pituitary peptides (Mallinckrodt Package Insert, 2019) currently approved for the treatment of ocular inflammatory conditions including keratitis. ACTH is a member of the family of structurally related peptides known as melanocortin peptides.

Melanocortin peptides, which include ACTH, as well as, α -, β -, and γ -melanocyte stimulating hormones, are derived from the natural protein pro-opiomelanocortin and exert their physiologic effects by binding to cell surface G-protein coupled receptors known as melanocortin receptors (MCRs) ([Mountjoy, 1992](#)). Five subtypes of MCRs have been identified to date (MC1R to MC5R), each with different tissue distributions, binding affinity characteristics, and physiological roles ([Getting, 2006](#)) ([Montero-Melendez, 2015](#)). ACTH binds to all 5 subtypes of MCR ([Schioth, 1995](#)).

A detailed description of the chemistry, pharmacology, efficacy, and safety of Acthar is provided in the ([Acthar® Gel Package Insert, 2019](#))

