1.2. Study Rationale

Noninfectious keratitis can result from many different etiologies including systemic autoimmune disorder. Inflammatory cells express melanocortin receptors (MCRs) and anecdotal evidence suggests that Acthar Gel, a MCR agonist, is beneficial in treating ocular inflammation and alleviating the associated symptoms ([Perez, 2019](#)). Acthar is believed to exert its immunomodulatory effect through the activation of multiple MCRs present in immune cells, as well as in the eye, and the adrenocortex. The introduction of Acthar to the treatment algorithm for keratitis may provide a treatment option when early treatments have failed or were not well tolerated.

The study is being conducted to explore the efficacy and safety of Acthar in subjects with severe keratitis to better understand how different clinical parameters observed within the spectrum of this condition might be impacted by treatment with Acthar® Gel.

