8.2. Populations for Analysis

For the purposes of analysis, the following populations are defined

- The Modified Intent-to-Treat (mITT) population will include all subjects who receive at least 1 dose of study drug and who contribute any postbaseline efficacy data to the study.
- The Per-Protocol (PP) population will include a subset of the mITT population with subjects who do not have any major protocol deviations.
- The Safety Population will include all subjects who receive 1 or more doses of study drug.

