8.3.1. Efficacy Analyses

All efficacy analyses will be performed on the mITT population. Selected analyses may be performed on the Per-Protocol population.

Baseline and change from baseline at each posttreatment visit will be summarized for all numerical variables with descriptive statistics. Frequency and percentage will be calculated for categorical variables. The nominal p-values along with the 95% confidence intervals (CI) will be provided as appropriate. For subjects who have both eyes affected, the change from baseline will be determined based on the eye with the worst severity at baseline. If both eyes have the same severity at baseline, the right eye will be used to determine change from baseline.

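### Exclusion 7 as written bars every subject who sees better than 0.7 logMAR in both eyes; either the sign is reversed or an inclusion criterion sits in the exclusion list

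*Combined protocol and SAP*

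**What the plan says.** The header of Section 4.2 sets the logic for the whole list: "A subject is ineligible for study participation if the subject meets any of the following criteria at the Screening or Baseline Visit". Item 7 of that list is "Have best corrected visual acuity < 0.7 Logarithm of the Minimum Angle of Resolution (logMAR) in each eye at the Screening and Baseline Visits".

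Section 4 closes off discretion at entry: prospective approval of deviations from the enrolment criteria, "also known as protocol waiver or exemption, is not permitted".

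The abbreviation list expands logMAR as the logarithm of the minimum angle of resolution. Section 7.1.1 has best corrected visual acuity (BCVA) measured on an ETDRS chart. No other section restates, explains or corrects the 0.7 limit. Inclusion 6 in Section 4.1 defines ocular severity by corneal and conjunctival staining, redness, Schirmer score and Ocular Discomfort Score, and sets no acuity requirement.

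**The concern.** A smaller logMAR value means that a smaller angle can be resolved, which is better vision. An exclusion for values below 0.7 in each eye therefore removes the subjects who see well and keeps those who see badly. An acuity exclusion would ordinarily be expected to work the other way, and the protocol gives no reason for this one.

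What is at stake is who gets into the trial. A site that follows the text rejects otherwise eligible subjects with good acuity. A site that follows what it presumes was meant enrols subjects in breach of a criterion that cannot be waived. With approximately 6 sites planned, different sites may presume different things. Subjects enrolled in this way could also be classed as major deviators and drop out of the Per-Protocol set, which Section 8.2 defines as a "subset of the mITT population with subjects who do not have any major protocol deviations" without defining major.

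**Working it through.** **Inputs.** The list logic and item 7 come from Section 4.2, the meaning of logMAR from the abbreviation list, and the planned numbers from Section 8.1. The plan gives no figure of its own to reproduce on this point.

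**Step 1: what 0.7 logMAR means.** The minimum angle of resolution is 10^logMAR arcmin, and the Snellen denominator is 20 times that angle.

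- 0.0: 10^0.0 = 1.00, or 20/20
- 0.3: 10^0.3 = 2.00, or 20/40
- 0.7: 10^0.7 = 5.01, and 20 × 5.01 = 100.2, or about 20/100
- 1.0: 10^1.0 = 10.0, or 20/200

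Values below 0.7 are therefore better than about 20/100.

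**Step 2: the rule as written and the candidate repairs.** The table gives eligibility on this item alone, for five illustrative pairs of eyes in logMAR, with the same values at both visits.

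| Rule | 0.1, 0.1 | 0.1, 0.7 | 0.1, 0.9 | 0.7, 0.7 | 0.9, 0.9 |
|---|---|---|---|---|---|
| As written: excluded if both < 0.7 | OUT | in | in | in | in |
| Sign reversed, both eyes: excluded if both > 0.7 | in | in | in | in | OUT |
| Sign reversed, either eye: excluded if any > 0.7 | in | in | OUT | in | OUT |
| Moved to inclusion: eligible only if both < 0.7 | in | OUT | OUT | OUT | OUT |

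Only the written rule rejects the subject with two good eyes. The three repairs agree on the first and last columns and disagree on the middle three. Correcting the direction alone therefore does not settle the rule. On item 7's own visit wording, the written rule and the moved-to-inclusion rule are exact complements: whoever passes one fails the other.

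**Step 3: visit wording.** The header applies at Screening or Baseline, whereas item 7 says Screening and Baseline. A subject below 0.7 in both eyes at only one visit is excluded under the header and not under the item.

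**Step 4: does the protocol describe the literal population?** Section 1.2 says the study aims "to better understand how different clinical parameters observed within the spectrum of this condition might be impacted by treatment with Acthar". It does not ask for reduced acuity. Section 2.2 lists BCVA among the safety findings, and Table 2 of efficacy assessments omits it. Section 7.1.1 describes BCVA under the efficacy heading but gives no reason to require poor vision. The primary outcome in Section 2.3 is the IDEEL responder proportion, which is not an acuity measure.

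**Step 5: size.** The excluded share cannot be calculated without an acuity distribution. Section 8.1 plans about 36 screened for 30 analysable subjects, which leaves 36 − 30 = 6 losses from all causes (6/36 = 17%). If the literal rule removed more than 6 of 36 screened, it would break that plan on its own. Section 3.4 speaks instead of up to 36 enrolled, and on that basis this bound does not apply.

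**The case against.** The best defence is that item 7 is a deliberate severity gate. The trial is for severe or recalcitrant keratitis, and Section 1.1 says the disease "can result in partial or total loss of vision if left untreated". Requiring at least one eye at 0.7 or worse resembles the at-least-one-eye structure of Inclusion 6. Many entry criteria carry no stated rationale, an entry criterion need not be an efficacy endpoint, and the aim quoted from Section 1.2 concerns clinical parameters in severe keratitis and promises no particular range of acuity.

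Part of this stands: some target subjects would pass the literal rule, and silence is not proof of error. But the rule is not tied to the eye that qualifies under Inclusion 6. A subject with 0.1 in the keratitis eye and 0.9 in the other eye for an unrelated reason passes. Exclusions 2 and 12 already remove several other causes of poor acuity, such as glaucoma, uveitis and wet macular degeneration, so the literal population would be narrow, and no section describes it.

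A second objection is that the scale label, rather than the sign or the list, could be wrong: below 0.7 would point to poor vision on a scale where higher is better. Nothing in the documents supports this, though the sponsor can confirm the scale when amending the item.

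A third objection is that the analysis is barely touched. That is largely right. Section 8.3.1 says "All efficacy analyses will be performed on the mITT population. Selected analyses may be performed on the Per-Protocol population", and a subject who is dosed and has postbaseline efficacy data stays in the mITT set whatever the entry breach. The case for correction rests on enrolment and on consistent application across sites.

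**Conclusion.** The concern holds. The text excludes every subject with BCVA better than 0.7 logMAR, about 20/100, in both eyes, and nothing elsewhere in the documents reverses that. It rests only on the documents' expansion of logMAR and the any-item logic of the list header.

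That this is a drafting error is an inference from the absence of any supporting rationale. It is strong but not certain, and which error occurred cannot be determined from the documents. The number of subjects affected is unknown. The item must be corrected because it is an eligibility rule that cannot be waived and that, followed literally, enrols a population the protocol does not describe.

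**What to change.** The sponsor should first state the intent of item 7 and then amend it. If good acuity was not meant to be excluded, either write the limit in words, so that the direction cannot be misread, or move the item to the inclusion list. Either way, the amended text should state:

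1. the direction of the limit;
2. whether one eye or both must meet it;
3. how a value of exactly 0.7 is treated;
4. whether it applies at Screening, at Baseline, at either or at both, consistently with the list header.

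If excluding good acuity is intended, the rationale and objectives should say so and explain why.

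The cost is a one-line protocol amendment with sponsor and IRB/IEC approval under Section 9.1.1, and an update of the matching eligibility checks. Any subject already screened under item 7 needs the eligibility decision checked against the clarified rule.
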